8.3 Definitions relevant to the classification of adverse events

Severity (serious/non-serious), also called seriousness (serious/not serious). Serious or serious is defined as any event that: results in death, threatens life, requires hospitalization or prolongs hospitalization, is a cause of permanent or significant disability or disability, is the cause of alterations or malformations in the newborn, other medically important conditions.

Severity (mild, moderate, or severe). Mild is those that present with minimal symptoms, do not require treatment or suspension of the medication; moderate, when they interfere with usual activities, without threatening the patient's life, require treatment and may or may not require discontinuation of the medication; severe, those that interfere with usual activities and require pharmacological treatment and discontinuation of the medication.

Causality. It is the relationship that is assigned between the drug and the AE: certainly caused by the drug, there is clear evidence of causality, i.e. the AE reappears with the administration of the drug; probably caused by the drug, there is a high suspicion of causality but there is no direct evidence or it is considered unnecessary or dangerous, i.e. the reaction disappears when the drug is stopped; possibly caused by the drug, there is additional information to suggest that the cause may be due to another drug or disease; unlikely to be caused by the drug, there is a clear explanation of the origin due to the underlying disease or the use of another drug; conditional, there is a lack of data to issue a clear causality; unclassifiable, those for which, once all possible information about the EA has been obtained, it remains unclassifiable.

8.4 Responsibilities of the researcher

It is the responsibility of the Investigator to verify AEs through questioning, review of the information recorded in the patient's diary, pertinent physical examination, assessment of evolution, as well as appropriate medical and pharmacological management; as well as to follow up until the resolution or outcome and definitive discharge of the AE, following the definitions determined in national and international regulations. [51] [52] [53]

In the event of AEs or any event that puts the health and well-being of patients at risk, relevant medical care will be provided, either at the research center or referred to the Hospital Center with the greatest resolution power with which the research center has a medical care agreement. The PI will notify the sponsor's clinical monitor, according to the times established in national and international regulations. In the case of serious AEs, it will notify the sponsor and register the corresponding information in the FRCE and in turn, inform the IEC and IC.

The attention of the AEs will be carried out according to the event attention diagram. See [Figure 6 Adverse Event Care](#).

The final report to be written by the Clinical Team of the Medical Management Department of Laboratorios Sophia, S.A. de C.V., will include the report of the AEs in compliance with current national and international regulations. [52] [51]

If the research patient debuts during their participation in the study with a chronic AE, such as diabetes or systemic arterial hypertension, they will be referred to the competent health professional for chronic treatment. The follow-up and termination of your participation will be in accordance with the stipulations of the ICH.

8.4.1 Record of adverse events in the electronic case report form

EA registration considers:

- The patient's identifying information such as: code, age, gender, left eye, right eye.
- Information about the type of AE to the PI or the drug under study, as appropriate.
- Important date information:
 - Date the EA occurs
 - Date on which the PI becomes aware of it
 - Date of resolution or outcome, as applicable.
- Information on diagnosis and clinical management. If a lack of therapeutic response to the PI and/or investigational drug is detected, it must be reported as a serious AE within the period stipulated by current regulations. Include in concomitant medications the therapy used for the pharmacological management of AEs.

Record the outcome or resolution of the event:

- Recovered patient without sequelae
 - Recovered patient with sequelae
 - Patient not recovered
 - Patient who died due to AE
 - Patient who died and it is judged that the drug may have contributed
 - Patient who had death and it is not related to the product or drug under investigation,
 - Or indicate that you do not know what the consequence of the event is.
- Information about the investigational product or drug or the drug associated with the EA, AMR, or SRAM. As applicable, the information concerning the generic name, distinctive name or code of the IP and/or investigational drug must be recorded, as appropriate according to the methodological design of the study, this is relevant in the case of blinded studies or in those where placebo is used as comparators, since there are circumstances that justify the opening of the blinded to determine if the AE may be attributable to the active agent. the combination of active agents, or the pharmacologically inert substance(s), such as vehicles or additives, as appropriate to the phase of clinical research in which the development of the drug is located. It will also be necessary to include the data concerning the batch number, manufacturing laboratory, expiration date, dose, route of administration, start and end dates of administration and/or consumption, reason for prescription; according to whether it is an investigational product or drug (protocol in which the patient currently participates) or is a drug that the investigational patient consumes for the treatment of underlying concomitant diseases or uses for the management of some transitory sign or symptom that does not correspond to the Natural History of the pathology that motivated his or her entry into the research protocol.
- Indicate the withdrawal or maintenance of the investigational drug, PI, or drug, as appropriate. Indicate whether withdrawing the PI or investigational drug or suspected drug (of causing the event) makes the EA disappear. Also indicate if a dose adjustment is made, if the event changes in terms of intensity or seriousness, persistence of the reaction. It is important to indicate whether in those patients who are exposed again to the PI, investigational drug or drug, which had previously been discontinued, the AD reappears.
- Information regarding concomitant pharmacotherapy. Indicate the generic name, dose, route of administration, start and end dates of use, as well as the reason for the prescription, regardless of whether it is in accordance with the prescribing information or technical data sheet or is used outside the regulations or what has been authorized by the local, national or international regulatory entity.

[figure not shown]
- Relevant medical history information. The analysis of the EA considers the information previously narrated, despite the clinical context in which this harmful phenomenon occurs in the participants of the clinical research protocol, is of special interest, so the information about previous conditions, hypersensitivity or allergy phenomena, previous surgical procedures, laboratory analyses or cabinet examinations that have been performed on the participant, etc., that the researcher deems it appropriate to mention may do so.

8.4.2 Adverse Event Tracking

The PI will provide the attention and management of the EA presented by the participant until the outcome of the same, according to what is referred to in the following section.

8.4.3 Procedures for a serious adverse event

The AE care process considers the following stages:

During the development and conduct of this study, undesirable harmful events or adverse reactions of medical implication may occur in the investigational patient, which do not necessarily have a causal relationship with the PI or investigational drug. These harmful phenomena can occur during the use of investigational drugs at doses authorized for use in humans by a local, national

or international regulatory entity. However, it may be suspected that the PI or the investigational drug causes some unwanted clinical manifestation. AEs, ADRs or SRAMs to one or more medications can occur during the systematic evaluation of the participants (on the days when the clinical review is scheduled, according to the schedule of activities) or suddenly, in such a way that:

1. The investigator must be the first person to whom the patient notifies that he or she has developed or presented any harmful phenomenon of a clinical nature during his or her participation in this study.
2. According to his clinical judgment, Based on the pertinent physical examination, interrogation, etc., as well as the analysis of the information available in the medical literature and what is referred to in the Investigator's Manual, Information to prescribe or Summary of the Comparator Drug Label, the principal investigator determines the pertinent care of the harmful event/reaction.
3. Such care can be in the research center or in the hospital with the greatest resolution power. In such a way that, in the event that the patient is sent by the PI to a hospital, he or she attends through a referral system. The referral can be with a card that identifies the patient as a study participant and links him or her to the pre-established agreement with the institution, or through a medical reference note issued by the PI. Laboratorios Sophia, S.A. de C.V., will pay the expenses for the medical care of the participating patient, when the EA is associated with or is in relation to the PI or investigational drug.
4. Taking the clinical information collected, either during the care provided at the research center or that provided by the treating physician(s) in the hospital, the PI will record the AE in its clinical note, stating the seriousness, intensity (mild, moderate or severe) and relationship with the product or drug under investigation.
5. The PI must migrate the relevant data to the FRCE and its respective EA section. By, in cases of severe AEs, which must be notified in less than 24 hours after the PI becomes aware of it, the clinical monitor of the study is informed, so that in turn it informs the Clinical Team and the Pharmacovigilance and Technovigilance Unit of Laboratorios Sophia (UTFLS), so that it can later inform the CEI. With respect to non-serious AEs, they will be registered and treated appropriately, and the corresponding regulatory entity will be informed about the safety profile of the PI or investigational drug in the final report of the clinical trial

The recording of the outcome of the AE depends substantially on the follow-up that the PI performs on the patient, since it is expected that most of the harmful phenomena (see section of the safety profile in the investigator's manual) are ophthalmic in nature, however, there may be systemic alterations. Therefore, in the opinion of the researcher, the withdrawal of the participant or their permanence will be considered.

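### The 24-hour notification rule in section 8.4.3 is worded for severe rather than serious adverse events; separately, the intensity grades in section 8.3 overlap and leave a gap

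*Combined protocol and SAP*

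**What the plan says.** **Definitions (8.3).** Two attributes are defined. The first is introduced as "Severity (serious/non-serious), also called seriousness (serious/not serious" and rests on outcomes such as death, threat to life, hospitalisation and disability. The second, also headed with the word severity, is intensity:

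- Mild: minimal symptoms, with neither treatment nor suspension needed.
- Moderate: interferes with activities without threatening life; such events "require treatment and may or may not require discontinuation of the medication".
- Severe: "severe, those that interfere with usual activities and require pharmacological treatment and discontinuation of the medication".

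**Recording (8.4.3, step 4).** The investigator writes a clinical note "stating the seriousness, intensity (mild, moderate or severe") and the relationship to the product. The two attributes are recorded separately.

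**Notification (8.4.3, step 5).** Under the title "8.4.3 Procedures for a serious adverse event", the clock applies "in cases of severe AEs, which must be notified in less than 24 hours after the PI becomes aware of it". The next sentence gives the alternative: "With respect to non-serious AEs, they will be registered and treated appropriately", with the regulator informed through the final report.

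**Other notification rules.** Section 8.1 places AE reporting under the national norm and ICH guidance. Section 8.4 says "In the case of serious AEs, it will notify the sponsor and register the corresponding information in the FRCE", and that the investigator also informs the committees. It states no hours; for notifying the clinical monitor it refers to regulatory times. Section 8.5.1 gives 24 hours to unanticipated problems that are serious AEs and 5 business days to other unanticipated problems.

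**The concern.** The two branches of step 5 are not complements: one is defined by intensity and the other by seriousness. An event can be serious without being severe, or severe without being serious, and 8.3 and step 4 of 8.4.3 both allow for this. A site that follows the wording could give a serious, moderate event no fixed deadline and could treat a severe, non-serious event under two instructions at once.

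What is at stake is how quickly serious events reach the sponsor. Section 11.3 lists serious AEs in more than 10% of a study group as a ground for considering suspension or early termination, and that count is only as current as the notifications behind it.

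The grading definitions are a second, independent matter. Intensity is a listed AE measure in the variable table of 7.4.4. If one event can properly be given either of two grades, or none, the intensity tables depend on who completes the form.

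**Working it through.** No sample size, power or alpha figure is involved, so the check is an enumeration of the text.

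**1. The clock.** Cross seriousness (2 levels), intensity (3 levels) and unanticipated-problem (UP) status (2 levels): 2 × 3 × 2 = 12 event types. Apply the rules literally.

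| Event type | Number of types | 24-hour branch, 8.4.3 step 5 | Non-serious branch, 8.4.3 step 5 | 8.5.1 |
|---|---|---|---|---|
| Serious, mild or moderate, not UP | 2 | no | no | does not apply |
| Serious, mild or moderate, UP | 2 | no | no | 24 hours |
| Serious, severe, not UP | 1 | yes | no | does not apply |
| Serious, severe, UP | 1 | yes | no | 24 hours |
| Non-serious, severe, not UP | 1 | yes | yes | does not apply |
| Non-serious, severe, UP | 1 | yes | yes | 5 business days |
| Non-serious, mild or moderate, not UP | 2 | no | yes | does not apply |
| Non-serious, mild or moderate, UP | 2 | no | yes | 5 business days |

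The types sum to 2 + 2 + 1 + 1 + 1 + 1 + 2 + 2 = 12. Of the 6 serious types, 4 have a stated 24-hour limit and 2 do not. Those 2 still carry the duty in 8.4 to notify the sponsor. Of the 6 non-serious types, 2 fall in both branches of step 5.

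**2. Whether the uncovered types can occur.** Section 8.5 requires all three of its criteria for an unanticipated problem: unexpected, related or possibly related to participation, and indicative of greater risk than previously recognised. An unrelated hospitalisation fails the second. Section 8.4.1 also directs that lack of therapeutic response be reported as a serious AE within the regulatory period, and 7.4.4.2 treats an OSDI rise of at least 40% from baseline as an AE for lack of efficacy. Such an event need not meet the 8.3 description of severe. Because the protocol foresees it, it may not count as unanticipated either.

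**3. With the trigger reworded to serious.** All 6 serious types carry a 24-hour limit, none of the 6 non-serious types does under step 5, and no type falls in both branches.

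**4. The grades (8.3), checked on their own.**

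- *Overlap.* Take an event that interferes with activities, does not threaten life, needs drug treatment and needs discontinuation. It meets moderate, where discontinuation is optional, and it meets severe, where discontinuation is required.
- *Gap.* Take an event that needs discontinuation but no treatment. Mild excludes suspension, and moderate and severe both require treatment. It meets none.

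Rewording the clock (item 3) would leave both of these in place.

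**5. Who informs the ethics committee.**

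| Section | Route | Time limit |
|---|---|---|
| 8.4 | Investigator informs the committees of serious AEs | No hours stated |
| 8.4.3 step 5 | Clinical monitor, then the sponsor's clinical team and pharmacovigilance unit, then the ethics committee | Later; no limit stated |
| 8.5.1 | Investigator to ethics committee and sponsor | 24 hours if serious, 5 business days otherwise (unanticipated problems only) |

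**The case against.** The best reply is that *severe* in step 5 simply means *serious*. The section title says serious, the contrasting sentence says non-serious, and 8.3 itself uses severity as a label for seriousness. On that reading the branches are complements and items 1 and 2 of the working fall away. This is the likelier intention, and it rules out treating the wording as a deliberate intensity-based rule. It does not remove the need for correction, because step 4 has just told the investigator to record intensity with the word severe as one of its values.

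A reader might infer more than the documents support:

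- *That serious events of lesser intensity have no 24-hour rule anywhere.* Section 8.5.1 gives 24 hours to any serious AE that is an unanticipated problem, whatever its intensity.
- *That a severe non-serious event has two 24-hour rules.* It has one, plus the non-serious branch. The two can both be obeyed: the first informs the monitor and the sponsor's units, the second the regulator in the final report. The literal result is over-reporting to the sponsor.
- *That the overlapping grades cause the gap in the clock.* The single word severe causes it. The overlap only blurs the trigger at the boundary between moderate and severe.
- *That serious events would go unreported and the 11.3 criterion would fail.* Section 8.4 sends every serious AE to the sponsor. What is missing for some is a stated number of hours.
- *That open-label treatment would bias the grading.* The documents offer no evidence of this. The safety variable in 7.4.3 is the incidence of unexpected, product-related AEs; intensity is a descriptive item in 7.4.4.

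It is also fair to say that the ethics committee routes in 8.4 and 8.4.3 could run in parallel. They are unreconciled rather than shown to be incompatible.

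**Conclusion.** The point holds as an inconsistency of terminology in an operative safety rule. Read literally, 2 of 12 event types (serious, mild or moderate, not an unanticipated problem) have a duty to notify, partly by reference to regulatory times, but no stated 24-hour limit. Another 2 (non-serious, severe) sit in both branches of step 5. The effect on the 11.3 criterion is limited to an unspecified notification time for the first group. The counts are of event types, not of expected events; the documents give no basis for estimating how often each would arise.

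The grading defect in 8.3 stands separately and does not depend on how step 5 is read: there is at least one overlap and at least one gap.

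Neither matter touches the primary efficacy analysis. The conclusion on the clock assumes that sites apply severe as 8.3 defines it for intensity. If every site reads it as serious, the practical effect is nil and only the wording needs repair.

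**What to change.** 1. In 8.4.3 step 5, replace *severe* with *serious (as defined in 8.3, whatever the intensity)* and keep the non-serious branch as its complement.
2. In 8.3, reword the intensity grades so that every event fits exactly one. The sponsor must decide where the boundary between moderate and severe lies and where an event that needs discontinuation without treatment belongs. Using severity for only one of the two attributes would also help.
3. Reconcile 8.4, 8.4.3 and 8.5.1 on which party informs the ethics committee of a serious AE and within what time.

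The cost is wording in a few paragraphs and matching text in the eCRF completion guide. No visit, measurement or procedure is added.

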8.4.4 Causation assessment

Causality assessment is the methodology used to estimate the probability of attributing the observed AE to a drug, investigational drug or IP. It considers probabilistic categories according to the available evidence and the quality of the information, based on national pharmacovigilance regulations. [51]

The UFTLS can use the algorithm of Karch and Lasagna modified by Naranjo referred to by Aramendi I, as a tool to facilitate the probabilistic categorization of causality. In this algorithm, different items are scored, which allow assigning a value to the cause-effect relationship between the administration of the drug and the adverse reaction. [54] See Appendix 16.4 Karch and Lasagna algorithm modified by Naranjo.

In such a way, the degree of certainty to establish the PI or investigational drug (as appropriate) as the causal agent of the harmful phenomenon that occurs to the patient of the clinical study. It can also be indicated directly by the PI based on their clinical experience or through the voluntary application of the tool mentioned above. However, it is important for the researcher and the UFTLS to consider the following arguments in favor of causation:

- a. Strength of association, which refers to the number of cases in relation to those exposed.
- b. The consistency of the data, i.e. the presence of a common characteristic or pattern.
- c. The exposure-effect pattern, which determines the relationship with the site of appearance, time, dose and reversibility after deletion.
- d. Biological plausibility, which refers to the possible pharmacological or pathophysiological mechanisms involved in the development or presentation of the adverse event.
- e. Experimental findings, e.g., the appearance of abnormal metabolites or high levels of the drug or its biotransformation product.
- f. Analogy, which refers to the experience gained with other related drugs, adverse reactions frequently produced by the same family of pharmacological agents.
- g. Nature and characteristics of the data, i.e. objectivity, accuracy and validity of the relevant documentation. [55]

8.5 Unanticipated Issues

Unanticipated problems (APNs) consider those situations that pose risks to participating patients, in general, any incident, experience or outcome that meets all the following criteria:

- Unexpected in terms of its nature, severity, or frequency in relation to 1) study-related documents such as the investigator's manual, study protocol, and informed consent form; and 2) the characteristics of the population being studied.

- Related or possibly related to your participation in the study (possibly related means that there is a reasonable possibility that the incident, or results, was caused by study procedures).
- Indicative that the research places participants at a higher risk of harm (including physical, psychological, economic, or social) than previously recognized.

8.5.1 PNA Report

The PI will be responsible for reporting NAPs to the sponsor, IC, CEI. The report must contain the following information:

- Identification of the study: protocol title and number, name of the PI and, if applicable, of the centre.
- Detailed description of the event, incident, experience, or outcome.
- Explanation, justification of the reasons why the incident represents a NAP.
- Description of changes to the protocol or corrective actions taken or proposed in response to the NAP.

NAPs that are SEA must be reported to the IEC and the sponsor within the first 24 hours of the PI becoming aware of it.

Any other NAPs will be reported to the CEI and the sponsor within the first 5 business days after the PI became aware of it.

9. Study Monitoring

The study sponsor is responsible for monitoring the study. Monitoring activities include, but are not limited to general safety monitoring, general study quality monitoring, monitoring by study site, detection monitoring, reporting and tracking of AEs, monitoring for resolution of discrepancies in data capture, etc.

Responsibility for monitoring activities and ultimate responsibility for monitoring rests with the sponsor.

The details of the monitoring activities are specified in a separate document from this protocol in a Monitoring Plan.

